11.5. Efficacy Analyses

For the Double-Blind Treatment Period, the primary and secondary endpoints will be analyzed using the FAS. Other important statistical considerations, such as handling rescue medication/rescue procedure uses during study treatment, missing data imputation strategies, sensitivity analyses, and subgroup analyses will be described in the SAP.

The endpoints of percentage change in esophageal PEC from Baseline to Week 16 and Week 24 will be analyzed using analysis of covariance (ANCOVA) model based on rank scores due to the skewed distribution of the data and possible outliers. The ANCOVA model will include treatment group and randomization stratification factors as factors and Baseline eosinophil PEC as a covariate. PEC after rescue medication/rescue procedure uses will be set to missing; all missing data will be imputed in the FAS using MI procedure as appropriate. Multiple results of ANCOVA (least square [LS] mean rank scores and LS mean rank score difference from placebo) for each MI dataset will be analyzed and reported along with final p-value using Rubin's method [1]. In addition, a descriptive summary of percentage change in esophageal PEC from baseline as well as the difference between treatment groups will be presented by treatment group. When applying the same ANCOVA model to key secondary continuous variables, norank transformation will be used.

For the efficacy endpoints of the percentage change in esophageal PEC from Baseline at Week 16 and Week 24, in the FAS, subjects who have experienced intercurrent events, such as rescue medication/rescue procedure use, early discontinuation of study treatment, etc., will be included in the analysis and their missing data at Week 16 and Week 24 will be imputed using a MI model. The MI model will take into consideration the reason and nature of intercurrent event leading to missing data. A detailed plan for constructing and analyzing the primary estimand will be described in the SAP.

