3.3. CHANGES TO ANALYSIS FROM PROTOCOL

- Not applicable.

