8.3. MISSING DATA

Missing adverse event (AE) relationship to study drug and AE seriousness will be imputed as described in Section 17.1.1.2 and 17.1.3, respectively. Partial or missing AE start dates, Concomitant Medication (CM) start dates, and hospitalization dates will also be imputed as described in Appendix 2. No other missing safety data will be imputed.

Missing efficacy data will be handled as described in Sections 16.1.2, 16.2.2, and 16.3.2. In the primary analysis of the primary endpoint, PEC after rescue medication and/or rescue procedure uses will be set to missing; all missing data will then be imputed in the FAS using multiple imputation. In the main analyses of all binary responder-type endpoints, all subjects with missing data, regardless of reason for missingness, will be considered as nonresponders. In the main analysis of continuous or score endpoints, subjects with missing data will be handled using observed cases only, multiple imputation, or a linear mixed effect model.

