17.1.2. MISSING DATA METHODS FOR PRIMARY EFFICACY VARIABLE

Subjects who 1) discontinue the study for worsening of disease, lack of efficacy, or adverse event related to EoE, 2) use a rescue medication for EoE, or 3) have rescue medical procedure during the study as confirmed after blinded review by clinical and medical team members before study unblinding will be considered to have a missing outcome in the analysis of all efficacy endpoints at any subsequent timepoints, including the primary endpoint. The rescue medications/rescue medical procedure will be identified by the Pfizer clinical team during blinded data review. The detailed information regarding the identification of rescue therapy is provided in Appendix 4. In scenarios 2 and 3 above, if a subject has an efficacy measurement collected after the initiation of rescue medication/rescue medical procedure, the observed data will be censored at the time of initiation and they will be considered as having a missing outcome. Subjects in all 3 scenarios above may still be included in the respective Per Protocol Set, provided they do not violate other criteria for Per Protocol Set. For example, they will be excluded from the respective Per Protocol Set if they initiate a prohibited medication before the Week 16 efficacy assessment that can affect efficacy of the study treatment and the indication is unrelated to EoE.

Analysis visits will be mapped as per Section 6.4 before any missing data imputation method is applied.

Subjects who initiate rescue medication will have PEC results after the start of rescue medication/rescue medical procedure set to missing. All missing PEC at Week 16 and Week 24 will then be imputed using multiple imputation under missing at random (MAR) procedure with a fully conditional specification (FCS) and predictive mean

matching for PEC as the primary missing data method. There are two different types of missing data patterns: non-monotone and monotone. A subject with missing data at any post-Baseline visit, and a non-missing data point after that visit is said to have intermittent missing data (non-monotone). A subject with missing data at any post-Baseline visit and at all subsequent visits is said to have monotone missing data.

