17.1.3. MULTIPLE IMPUTATION UNDER MAR

Any missing PEC at the planned assessments will be imputed using multiple imputation under MAR. MAR assumes the missing value is independent of unobserved outcomes given observed data (i.e., subjects with missing PEC can be modeled based on subjects with observed PEC values) (Rubin 1987).

The following steps will be implemented:

Step 1:

Regardless of the arbitrary missing data pattern (i.e. monotone or non-monotone), a fully conditional specification (FCS) method with predictive mean matching for continuous variables will be used to impute the missing PEC data. The FCS method allows for separate conditional distributions for each imputed variable. The predictive mean matching approach creates a regression model using parameters sampled from the posterior distribution and then a predicted value for each missing value is computed. The missing value is replaced by randomly selecting an observation from a set of 'k' values that are the closest predicted values to the missing predicted value. Missing data imputation will be performed using the SAS PROC MI procedure. The number of imputations will be 40. A separate imputation model will be used for each treatment group. The stratification variables will be included in the imputation models.

Step 2:

Percent change from Baseline in PEC will be re-computed at Week 16 for each of the 40 imputed datasets.

Step 3:

The analysis of covariance (ANCOVA) model based on rank scores including treatment group, reported randomization stratification factors of Baseline history of esophageal dilation (Yes/No) and concurrent PPI therapy (Yes/No) as factors and Baseline eosinophil PEC as a covariate will be run for each of the 40 datasets to obtain 40 estimators of interest.

Step 4:

Use SAS PROC MIANALYZE to produce an overall pooled estimate (mean of 40 estimates) with its associated standard error, confidence interval, and pooled p-value.

There could be certain adjustments to the multiple imputation model due to unexpected data issues after unblinding

treatment. All post-unblinding modifications to the multiple imputation model or approaches to address missing data will be described in the Clinical Study Report (CSR).

Additionally, missing data will be imputed using the following missing data methods: Tipping point analysis and observed data only. More details are provided in Section 16.1.5.

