17.1.4. PRIMARY ANALYSIS OF PRIMARY EFFICACY VARIABLE(S)

The following hypotheses (H01 and H02) for the primary endpoint will be tested:

H₀₁: The percentage change from Baseline in esophageal PEC at Week 16 is the same between etrasimod 2mg and placebo.

H₁₁: The percentage change from Baseline in esophageal PEC at Week 16 is different between etrasimod 2mg and placebo.

H₀₂: The percentage change from Baseline in esophageal PEC at Week 16 is the same between etrasimod 1mg and placebo.

H₁₂: The percentage change from Baseline in esophageal PEC at Week 16 is different between etrasimod 1mg and placebo.

All hypotheses will be tested at the 2 sided α level, 0.05.

The primary efficacy analysis will be performed for the FAS. Percent change from baseline in esophageal PEC will be summarized using the number of observations, mean, standard deviation (SD), median, minimum, and maximum. An analysis of covariance (ANCOVA) model based on rank scores due to the skewed distribution of the data and possible outliers will be used. The ANCOVA model will include treatment group and randomization stratification factors of Baseline history of esophageal dilation (Yes/No) and concurrent PPI therapy (Yes/No) as factors and Baseline eosinophil PEC as a covariate. Multiple results of the ANCOVA model will be expressed as least square (LS) means rank scores, LS mean rank scores difference from placebo, 95% confidence interval (CI) and p-value. For the treatment comparisons of etrasimod 1 mg vs. placebo and etrasimod 2 mg vs placebo, the treatment group factor in the ANCOVA model will include placebo, etrasimod 1 mg and etrasimod 2 mg. For the comparison of etrasimod any dose vs placebo, a separate ANCOVA model based on rank scores will be used, where treatment group factor will only include placebo and etrasimod any dose treatment. For the Extension Treatment Period, no pair-wise comparison will be performed; only descriptive statistics will be provided. In addition, descriptive summary of percentage change in esophageal PEC from baseline as well as difference between treatment groups will be presented by treatment group.

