17.1.6.1. Tipping Point Analysis

A tipping point approach based on multiple imputation of values through Week 16 will be used with a specified adjustment (referred to as delta adjustment or shift) applied to values imputed under a MNAR-based imputation model. To find a tipping point, a series of imputations will be performed with increasing values of delta.

The goal is to evaluate the plausibility of the assumed expected values for missing outcomes on each treatment group under which the conclusions change, ie, under which values of delta there are no longer evidence of significant treatment difference.

The following steps will be implemented:

Step 1:

Same as Step 1 described in 16.1.2 above.

Step 2:

Apply a shift (i.e. additive delta adjustment) to the imputed PEC at each visit in both treatment groups. Percent change from Baseline in PEC will be re-computed at Week 16 for each of the 40 imputed datasets.

Step 3:

Same as Step 3 described in 16.1.2 above.

Step 4:

Same as Step 4 described in 16.1.2 above.

Note, imputations with delta adjustment will be performed with progressively increasing delta values until a tipping point is reached based on the significance of the ANCOVA test based on rank scores. A tipping point will correspond to the smallest value of delta for which the primary hypothesis is no longer rejected. The shift parameter (delta) for the active treatment group will take increasing values from 0 with increments of 40 (maximum PEC of X), representing adjustments in towards worse outcomes (i.e., after dropout, on average, subjects on treatment will have PEC worsen). For placebo arm, delta adjustments will decrease with increments of 40, representing adjustments in the direction of better outcomes. The adjustments in each treatment group will be continued until the ANCOVA test based on rank scores for the primary hypotheses are no longer significant at the 2sided α level, 0.05. The corresponding shift parameters in both treatment groups at the tipping point will be reported along with the LS means rank scores, LS mean rank scores difference from placebo, 95% CI, and p-values from each ANCOVA test based on rank scores.

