
7-day period approach^b
	
DSQ total Score = (Sum of daily DSQ score with 7-day period preceding the scheduled visit day) ×7 / (Number of days with diaries reported with nonmissing* data within 7-day period).
 
Shifting rule when calculating DSQ total score at each visit based on the number of reported diary entries within the 7-day period prior to the visit:
 
Baseline visit and each post baseline visit: If there are less than 4 reported diary entries that are available within the 7-day period prior to the visit, then the most recent 4 reported diary entries in a consecutive 7-day period would be used to calculate the DSQ total score. In order to determine the most recent 7-day period with the minimum number of reported diaries, it may be necessary to make adjustments in some cases by shifting to earlier diary entries. Such 7-day periods cannot be shifted for more than 7 days (not including the study visit day). After shifting 7 days, if there are still less than 4 reported diary entries within the 7-day period, then the DSQ total score for baseline visit will be set to missing.
 
The DSQ total score range is 0 to 42
	
Same as 14-day period approach

^a Primary approach to calculate DSQ total score

^s Sensitivity approach to calculate DSQ total score

Change from Baseline in esophageal PEC at Week 16 will be based on the central EGD results.

Proportion of subjects with esophageal PEC < 15 eos/hpf and ≤ 6 eos/hpf at Week 16, will be based on central reading of the EGD results. Subjects who achieve esophageal PEC < 15 eos/hpf and ≤ 6 eos/hpf will be referred to as responders, respectively. Subjects who do not achieve esophageal PEC < 15 eos/hpf and ≤ 6 eos/hpf will be referred to as nonresponders, respectively.

Planned Analyses by Endpoint

Endpoint (at Week 16)	ANCOVA ^a / Weighted MH	Sensitivity Analyses: MI	Sensitivity Analyses: Tipping Point Analysis	Completer Sets and Per Protocol Set	Linear mixed effects model
Key primary endpoints					
Percent Change from baseline in esophageal PEC	X ^c	X ^e	X ^c	X ^c	
Key secondary endpoints					
Change from baseline in DSQ total score		X ^{e, f}	X ^{e, f}	X ^{e, f}	X ^{b, f, g}
Change from baseline in esophageal PEC	X ^c	X ^e	X ^c	X ^c	
Proportion esophageal PEC < 15 eos/hpf	X ^d	X ^e		X ^d	
Proportion esophageal PEC ≤ 6 eos/hpf	X ^d	X ^e		X ^d	

^a No rank transformation will be applied

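### The SAP's Planned Analyses table rules out ranking for the primary PEC endpoint and lists multiple imputation only as sensitivity, against SAP 17.1 and protocol 11.5

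*SAP*

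**What the plan says.** **Detailed text, primary endpoint.** SAP 17.1.4 states: "An analysis of covariance (ANCOVA) model based on rank scores due to the skewed distribution of the data and possible outliers will be used". SAP 17.1.3, Step 3, says that this rank-score model "will be run for each of the 40 datasets to obtain 40 estimators of interest". For missing values, SAP 17.1.2 names FCS imputation with predictive mean "matching for PEC as the primary missing data method". SAP 8.3 says the same of the primary analysis: "all missing data will then be imputed in the FAS using multiple imputation".

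**Protocol 11.5.** Percent change in PEC at Weeks 16 and 24 is analysed by rank-score ANCOVA in the FAS with MI. The exception is limited: "When applying the same ANCOVA model to key secondary continuous variables, norank transformation will be used".

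**Summary table, SAP 17.2.1.** The column headed ANCOVA / Weighted MH carries footnote a: "No rank transformation will be applied". The percent-change PEC row is marked in that column with footnote c, which sets post-rescue values to missing and does not mention imputation. The only column naming MI is headed as a sensitivity analysis; both PEC change rows are marked there with footnote e. The text below the table repeats percent change at Week 24 with the same ANCOVA model.

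**Declared changes.** SAP 3.3, "CHANGES TO ANALYSIS FROM PROTOCOL", has the entry that none apply.

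**The concern.** The table is the SAP's endpoint-by-endpoint list of what to run. For the primary endpoint it gives a different outcome scale from the section that defines the primary analysis, and it labels the primary missing-data method as sensitivity. The SAP states no rule on which text prevails.

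Followed as printed, the table would produce an unranked primary model. The tipping-point analysis in SAP 17.1.6.1 tests the rank-score model, so it would then be stress-testing a different analysis from the one reported. If the conflict is noticed only after unblinding, someone has to choose between two models whose p-values can fall on opposite sides of 0.05. The choice bears on a study whose primary objectives include selecting a dose.

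**Working it through.** The documents give no figure to reproduce, so the check is a comparison of passages, followed by an illustrative simulation.

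**1. Scope of footnote a.** It sits on the column heading and so covers every ANCOVA cell in the column. Of the five rows:

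| Row | Mark in the ANCOVA / MH column | Does footnote a fit? |
|---|---|---|
| Percent change in PEC (primary) | X, footnote c | No: SAP 17.1.3, 17.1.4 and protocol 11.5 require ranks |
| Change in DSQ | none (mixed model) | Not relevant |
| Absolute change in PEC | X, footnote c | Yes: protocol 11.5 |
| PEC < 15 eos/hpf | X, footnote d (MH) | Not relevant |
| PEC ≤ 6 eos/hpf | X, footnote d (MH) | Not relevant |

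The footnote is right for one row only, yet as placed it also governs the primary endpoint. With no change declared in SAP 3.3, it cannot be an announced departure from the protocol.

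**2. Status of MI.** For percent change, SAP 2.4 (primary estimand), 8.3 and 17.1.2 and protocol 11.5 all put MI in the main analysis. For absolute change in PEC, SAP 17.2.2 carries over the primary endpoint's missing-data methods, key secondary estimand 2 takes the primary estimand's handling, and 17.1.3 covers any missing PEC at planned assessments. The table names MI for both rows only as sensitivity.

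**3. What footnote c does and does not say.** It is silent on imputation but does not exclude it. It also marks the tipping-point cell, and SAP 17.1.6.1 describes that analysis as "A tipping point approach based on multiple imputation of values through Week 16". The MI part of the concern therefore rests on the column label, not on a stated prohibition.

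**4. Week 24.** The repeat refers to the same ANCOVA model directly below the table, so it inherits the ambiguity.

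**5. Illustrative size of the ranked versus unranked difference.**

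- From the documents: 96 subjects at 3:3:2, that is 96 × 3/8 = 36, 96 × 3/8 = 36 and 96 × 2/8 = 24; two-sided 0.05; a model with treatment, both stratification factors and baseline PEC.
- Assumed: baseline PEC log-normal with median 60 and log-SD 0.7, truncated at ≥ 15; Week 16 PEC = baseline × exp(effect + normal error), rounded; error SD 0.7, 1.0 or 1.2; 2 mg effect 0, −0.5, −0.8 or −1.2 log units, with 1 mg at half of that; two binary strata (40% and 50%) with no effect; no missing data.
- Method: 4,000 trials per setting, with ANCOVA on raw percent change and on its ranks.

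| Settings with an effect | 2 mg vs placebo | 1 mg vs placebo |
|---|---|---|
| Verdicts at p<0.05 differ | 0% to 32% | 11% to 27% |
| Ranked minus unranked power | 0 to +21 points | −6 to +0.4 points |

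Example, with error SD 1.0 and a 2 mg effect of −0.8:

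- 2 mg: power 82% ranked and 68% unranked (82 − 68 = 14 points); verdicts differ in 22% of trials.
- 1 mg: power 31% ranked and 34% unranked (31 − 34 = −3 points); verdicts differ in 21%.
- Simulation error on the 22% is about √(0.22 × 0.78 / 4,000) = 0.65 points.

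With no effect, both models reject in 4.4% to 5.7% of trials and disagree in 4.5% to 6.1%. MI versus no MI was not simulated.

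**The case against.** **Intent is clear.** The SAP revision history records that the primary model was updated to rank scores under protocol amendment 3.0, and every section describing the primary analysis agrees. The only contrary text is a footnote to a summary table placed in the secondary-efficacy section. Protocol 11.5 also names rank scores for Week 24 explicitly. On this view the defect is editorial. What stands is that intent is recoverable and the footnote is probably left over from an incomplete update. That shows which text is right; it does not correct the table.

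**The MI part is a label.** The sensitivity heading is correct for the two responder rows that share the column (protocol 11.4.2), and footnote c does not forbid imputation. This stands in part: for the primary row the MI conflict is weaker than the rank conflict. The label is still wrong for that row.

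**Absolute change in PEC is less settled.** SAP 8.3 allows observed cases, MI or a mixed model for continuous endpoints, 17.2.3.1 does not mention imputation, and the carry-over wording in 17.2.2 also covers DSQ, which uses a mixed model without imputation. This does not succeed. SAP 8.3 refers on to numbered sections (under old numbering, 16.2.2 for what is now 17.2.2), and 17.2.2 with estimand 2 points to MI. DSQ has its own explicit model and is a separate matter.

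**The size is assumed.** Both models hold type I error, p-values are unadjusted by design, and this is a Phase 2 study. This stands as a limit on the magnitude. It does not remove the contradiction.

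**Conclusion.** The concern holds. Footnote a states a rule that is wrong for the primary analysis, and the table mislabels MI for both PEC change rows. The rank conflict is direct; the MI conflict is one of labelling. Confidence in this reading is high, because it rests on the documents' own text and needs no assumption.

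The simulated disagreement rates do rest on the assumed PEC distribution, effects and complete data, and they say nothing about MI. They show only that the choice between ranked and unranked models can change a verdict under plausible conditions, and that neither model alone inflates type I error. Because the intended analysis can be recovered from the detailed sections, this should be fixed but does not undermine the plan.

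**What to change.** Before the Main Analysis unblinding:

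1. In the SAP 17.2.1 table, move footnote a from the column heading to the absolute-change PEC row. Write rank-score ANCOVA in the primary row's main-analysis cell and in the sentence on its Week 24 repeat.
2. Mark MI in the FAS (footnote e) as the main missing-data method for the percent-change and absolute-change PEC rows, and stop labelling it as sensitivity for those two rows. The heading can stay for the responder rows.

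The cost is a few words in one table, its footnotes and one sentence below it. No new data, outputs or programming are needed, since the change only brings the table into line with the SAP's own detailed text.

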17.2.2. MISSING DATA METHODS FOR SECONDARY EFFICACY VARIABLE(S)

The same missing data methods used for the primary endpoint described in Section 16.1.2 will be used for the continuous secondary efficacy endpoints. For proportion-based secondary endpoints, subjects with missing data for any reason or took rescue medication and/or rescue procedure will be considered a nonresponder.

17.2.3. PRIMARY ANALYSIS OF SECONDARY EFFICACY VARIABLES

17.2.3.1. Change from Baseline in DSQ total score and Esophageal PEC at Week 16

Analysis of the secondary efficacy variables change from Baseline in DSQ total score at Week 16 will use a linear mixed effect model. The linear mixed effect model will include treatment group, visit, interaction of treatment-by-visit, Baseline history of esophageal dilation (Yes or No), and concurrent PPI therapy (Yes or No) as factors and Baseline DSQ total score as a covariate using an unstructured covariance matrix. If there is a convergence issue in fitting the unstructured covariance, a compound symmetry covariance structure will be used. The Kenward-Rogers method will be used to estimate the denominator degrees of freedom. Change from Baseline in Esophageal PEC at Week 16 will use an ANCOVA model including treatment group and randomization stratification factors as factors and Baseline eosinophil PEC as a covariate. Eosinophil PEC assessments after rescue medication and/or rescue procedure use will be set to missing. LS means at visit and LS mean differences between treatment groups (i.e. etrasimod 1 mg vs placebo, etrasimod 2 mg vs placebo, and etrasimod pooled vs placebo) with p-values and corresponding 95% CIs will be reported. For the individual etrasimod summaries, treatment group will include placebo, etrasimod 1 mg and etrasimod 2 mg. For the pooled etrasimod summary, treatment group will include placebo and pooled etrasimod.

17.2.3.2. Proportion of Subjects with Esophageal PEC < 15 and ≤ 6 eos/hpf at Week 16

Analysis of the secondary efficacy variables proportion subjects with esophageal PEC < 15 eos/hpf at Week 16 and proportion of subjects with esophageal PEC ≤ 6 eos/hpf at Week 16 will be performed for randomization stratification factors of baseline history of esophageal dilation (Yes or No) and concurrent PPI therapy (Yes or No). Subjects who use rescue medication or have a rescue dilation, or with missing data at Week 16 for any reason will be considered nonresponders. The stratified analyses will be performed for randomization stratification factors. Results will be expressed as the number and percentage of subjects who achieved the goal, risk difference in

CCI [REDACTED]

- | [REDACTED]
- | [REDACTED]
- | [REDACTED]
- | [REDACTED]
- | [REDACTED]
- | [REDACTED]
- | [REDACTED]

CCI [REDACTED]

[REDACTED]

CCI [REDACTED]

CCI [REDACTED]	[REDACTED]	[REDACTED]	[REDACTED]	[REDACTED]
[REDACTED]			[REDACTED]	[REDACTED]
[REDACTED]				[REDACTED]
[REDACTED]		[REDACTED]		
[REDACTED]				[REDACTED]
[REDACTED]				[REDACTED]
[REDACTED]			[REDACTED]	
[REDACTED]			[REDACTED]	
[REDACTED]			[REDACTED]	
[REDACTED]			[REDACTED]	
[REDACTED]			[REDACTED]	[REDACTED]
[REDACTED]				[REDACTED]
[REDACTED]				[REDACTED]
[REDACTED]			[REDACTED]	
[REDACTED]			[REDACTED]	
[REDACTED]	[REDACTED]			

[REDACTED]

[REDACTED]

[REDACTED]

[REDACTED]

[REDACTED]

[REDACTED]

[REDACTED]

CCI [REDACTED]

[REDACTED]

CCI [REDACTED]

[REDACTED]

[REDACTED]

[REDACTED]

[REDACTED]

CCI [REDACTED]

[REDACTED]

[REDACTED]

[REDACTED]

